4.0 Background and Significance

Unintended pregnancy continues to be a major public health issue in the United States. In 2002, nearly half of the 6.4 million pregnancies in the United States were unintended.

Almost half of unintended pregnancies end in elective abortion. [9] Further, 80% of adolescent pregnancies are unintended.[10] The need for a highly effective, safe, estrogen-free, compliance independent and rapidly reversible contraception can be readily met with ESI. The etonogestrel subdermal implant has been available worldwide since 1998 and received United States Food and Drug Administration approval in 2006. Though studies have confirmed its efficacy, convenience, and cost-effectiveness, bleeding irregularities account for up to 43% of requests for early removal. [4, 11] though **the rate of 28.5% was reported in our population.** [29] Other reasons for removal include weight gain, headaches, mood changes and desire for pregnancy, each accounting for about 10-15% of removal requests.[11] Published data regarding bleeding management in US women is limited. A multicenter trial of 330 US women reported a 13 % removal rate for “bleeding pattern changes,” particularly within the first 8 months of use, consistent with international studies. [1, 2]. However, prior trials have excluded women weighing over 130% of ideal body weight [4]. Our retrospective study was the first US study to include women regardless of BMI.[3] Further, an expanded retrospective cohort of 337 women confirmed the efficacy of Doxycycline as 44% of women who received Doxycycline requested removal and 92% of those who received another intervention or declined intervention beyond reassurance requested removal [29]. A recent review of the literature includes interventions for bleeding but admits limited or anecdotal support for these. Further, the first line intervention contains estrogen, which is contraindicated in many ESI users [26]. The intervention in this proposed study is hormone-free.

Rationale for using Doxycycline as initial treatment for ESI related bleeding Doxycycline 100 mg twice daily for 10 days

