- Normal bleeding frequency (3-5 bleeding episodes).
- Frequent bleeding (more than 5 bleeding episodes),
- Prolonged bleeding (1 or more bleeding episodes lasting 14 days or more)

Subgroup analysis may provide additional insight into the efficacy of treatment for various bleeding patterns.

g. Patient satisfaction surveys

Patients will be asked to fill out short satisfaction surveys at randomization measuring satisfaction prior to any treatment, and at 13 and 26 weeks post randomization (see appendix). If patient has their ESI removed prior to 26 weeks post randomization, she will be given a final satisfaction survey at removal. Patient satisfaction surveys will be recorded on a paper formate or via Mayo Clinic website RED Cap.

Patients will rate their satisfaction with a) ESI and b) bleeding with ESI on a 5-point Likert scale ranging from very satisfied to very dissatisfied. If patient has ESI removed prior to 26 weeks post-study enrollment, she will be given a final satisfaction survey at removal.

h. Treatment issues

At enrollment, patients will be provided with a contact number allowing them to reach study personnel at all times with concerns. Instructions will be provided for instances of drug intolerance/allergy, heavy bleeding or other ESI related issues and clinical appointments for evaluation scheduled as needed.

i. Secondary Treatment

If a patient reports unacceptable bleeding at >4 weeks post randomization to treatment or placebo, study participation will be recorded as **need for additional treatment, and will represent the primary endpoint**. If she wishes to have secondary treatment, she will be treated with Doxycycline. Treatment will be limited to two interventions per 13 week

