interval to allow for assessment of efficacy of each course of Doxycycline. Rates of unacceptable bleeding in all patients remaining in the study at 26 weeks post-randomization will be calculated and participation in the study will end. If patients request ESI removal at any time during the study after randomly assigned treatment, study participation will be recorded as a **removal**. Method satisfaction will be assessed at removal and study participation will end. Patients will be provided with alternative contraception of choice at their expense. **Need for additional treatment at >4 weeks post-randomized treatment will represent the primary endpoint.** Satisfaction with ESI at randomization, and 13 and 26 weeks post randomization, and method continuation at 26 weeks post-randomization represent the secondary endpoints.

j. Post-treatment Followup

All patients will be contacted by study personnel at 26 weeks (\pm 2 weeks) post-randomization for final satisfaction survey and weight. Study completion BMI will be calculated. All diaries will be collected for analysis and patients will receive remuneration. When all patients complete the study, the data will be unblinded for analysis.

k. Special Considerations

If patients receive randomized treatment toward the end of the 39 week study interval (rather than at about 13 weeks post ESI insertion), post-treatment data for at least 13 weeks will be collected for a maximum study length of 52 weeks post-ESI insertion.

l. Additional testing

Additional laboratory testing or imaging for heavy or unusual bleeding will be individualized as clinically indicated.

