5.4.1 Power statements

Based on prior Mayo data, we anticipate about 30% of patients will develop unacceptable bleeding following ESI insertion.[3,29] These patients will be approached for participation in this study. The study plans to randomize a total of 100 patients with unacceptable bleeding to either placebo (N=50) or Doxycycline (N=50). The following calculations were based on a two-sided chi-square test with a type I error rate of 0.05.

Aim 1: Of the patients with bleeding concerns, based on our prior experience we anticipate that 44% of the patients randomized to Doxycycline will request additional treatment, and about 80% in the placebo arm. We are purposely overestimating the placebo effect over that noted in our cohort (92% removal requests) to allow for variation in the study group. Given the sample size of 50 per treatment arm, the study will have >90% power to detect the anticipated difference in the need for additional treatment.

Aim 2: Across the two arms, we anticipate that 66 of the 100 patients will request additional treatment and will receive additional treatment with Doxycycline. Within this subset we plan to estimate the method continuation rate following additional treatment. Based on a sample size of 66, the ½ width for a 95% CI around an estimate of 75% is ±10%.

Aim 4: Among the anticipated 66 patients who will request additional treatment for continued unacceptable bleeding at 26 weeks post-ESI insertion, we plan to quantify the patient satisfaction rate. If we assume 75% will be “very satisfied” or “satisfied”, then the ½ width for a 95% CI around this estimate will be ±10%.

5.4.2 Proposed Statistical Analysis:

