8.4 Impact of Expected results

The expectation of the study is that we will satisfy our hypotheses and find that

- **The failure of treatment, assessed as the requiring additional treatment, in the Doxycycline group will be statistically significantly lower than in the placebo group (primary endpoint)**
- The rate of removal for bleeding at 13 and 26 weeks post-randomized treatment will be lower in the Doxycycline group as compared to the placebo group though it may not be statistically significantly lower given the expected removal rate [3] and study sample size.
- **The rate of patient satisfaction at 13 and 26 weeks post-randomized treatment will be statistically significantly higher in the Doxycycline as compared to the placebo group**
- The incidence of associated symptoms, adverse events and treatment associated events will be low and consistent with prior studies
- No ESI-related contraceptive failures will be reported regardless of patient BMI.

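### A woman whose implant is removed for bleeding by week 4 cannot meet the primary-event definition in 5.3.1.i, and the plan does not say how any removal is scored in the primary comparison

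*Combined protocol and SAP*

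**What the plan says.** **Primary event.** Section 5.3.1.i sets the trigger: "If a patient reports unacceptable bleeding at >4 weeks post randomization to treatment or placebo, study participation will be recorded as". The status that follows is that the woman needs further treatment, and the section names this the primary endpoint. The same section repeats the 4-week floor in its closing statement of the endpoint.

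**Removal.** The same section continues: "If patients request ESI removal at any time during the study after randomly assigned treatment, study participation will be recorded as a" removal. Satisfaction is assessed at removal and participation ends.

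**Other statements of the endpoint.** Sections 2.0 and 5.3.2.A give the primary endpoint at 13 weeks without the 4-week floor. Section 8.4 also omits it ("The failure of treatment, assessed as the requiring additional treatment, in the Doxycycline group") and lists removal as a separate result: "The rate of removal for bleeding at 13 and 26 weeks post-randomized treatment will be lower in the Doxycycline group". None of the three says how a removed woman is counted.

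**Analysis.** Section 5.4.2 analyzes by randomized arm with a chi-square test. Kaplan-Meier and Cox methods are held in reserve in case follow-up is poor. Removal is not classified as an event, a non-event, missing, censored or competing. Section 8.3 acknowledges that removal can happen at any time and offers possible extra enrollment.

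**Planning rates.** Section 5.4.1 says "we anticipate that 44% of the patients randomized to Doxycycline will request additional treatment", against about 80% on placebo. It describes the 80% as "overestimating the placebo effect over that noted in our cohort (92% removal requests"). Section 4.0 gives the source: "44% of women who received Doxycycline requested removal and 92% of those who received another intervention" or declined intervention beyond reassurance.

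**The concern.** Removal because of bleeding is about the clearest failure of a bleeding treatment. Under 5.3.1.i, if it happens in the first 4 weeks it cannot be a primary event. After week 4, a removal request for bleeding would naturally also be a report of unacceptable bleeding, but the text does not say which status prevails.

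The analyst must therefore choose a rule, and the choices are not equivalent. Scoring the woman as a non-event records a failure as a success. Leaving her out selects the analysis set on something that happened after randomization. With 50 women per arm, a few such cases move the result. If the rule is chosen after unblinding, it can be chosen with the result in view.

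The planning rates add to the ambiguity. They come from removal requests in the cohort, but 5.4.1 labels them as requests for additional treatment, and its next paragraph has those women staying in the trial and receiving it.

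**Working it through.** **Inputs from 5.4.1:** 50 per arm; failure 44% on doxycycline and 80% on placebo; two-sided chi-square test; alpha 0.05. The documents give no rate of removal by week 4, so every early-removal figure below is an assumption.

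**Step 1: the plan's own figure.** Mean rate = (0.44 + 0.80)/2 = 0.62.
- SE under the null = √(2 × 0.62 × 0.38/50) = 0.0971.
- SE under the alternative = √(0.44 × 0.56/50 + 0.80 × 0.20/50) = 0.0902.
- Power = Φ[(0.36 − 1.96 × 0.0971)/0.0902] = Φ(1.88) = 97.0%.

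Exact enumeration of the uncorrected chi-square test also gives 97.0%. The statement of more than 90% is reproduced. The powers below use exact enumeration.

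**Step 2: early removals scored as non-events, equal share s of failures in each arm.** The observed rates become 0.80(1 − s) and 0.44(1 − s). Expected failures are 50 × 0.80 = 40 on placebo and 50 × 0.44 = 22 on doxycycline.

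| s (assumed) | Women lost as events, placebo / doxycycline (rounded) | Observed rates | Power |
|---|---|---|---|
| 0 | 0 / 0 | 80.0% vs 44.0% | 97.0% |
| 5% | 2 / 1 | 76.0% vs 41.8% | 94.9% |
| 10% | 4 / 2 | 72.0% vs 39.6% | 92.2% |
| 13% | 5 / 3 | 69.6% vs 38.3% | 90.2% |
| 14% | 6 / 3 | 68.8% vs 37.8% | 89.5% |
| 20% | 8 / 4 | 64.0% vs 35.2% | 84.7% |

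**Step 3: unequal numbers by arm (assumed), still scored as non-events.**
- 2 placebo, 0 doxycycline: 38/50 = 76% vs 44%; power 91.9%.
- 3 and 0: 37/50 = 74% vs 44%; power 88.0%.
- 4 and 1: 36/50 = 72% vs 21/50 = 42%; power 87.8%.
- 0 and 2: 80% vs 20/50 = 40%. The apparent difference rises from 36 to 40 points.

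The last case shows that the error need not be conservative. Suppose true failure is 70% in both arms, with early removals of 20 points on doxycycline and 10 on placebo scored as non-events. The observed rates are then 50% vs 60%, and the nominal 5% test rejects about 18% of the time.

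**Step 4: the same early removals under three rules, at s = 10%.**
- As failures: 80% vs 44%, difference 36 points, power 97.0%.
- As non-events: 72% vs 39.6%, difference 32 points, power 92.2%.
- Excluded: 46 placebo and about 48 doxycycline women. Rates are 0.72/0.92 = 78.3% and 0.396/0.956 = 41.4%, difference 37 points, power 96.2%.

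**Step 5: is the reason for an early removal recorded?** Section 2.0 documents the reason up to 26 weeks after enrollment, and enrollment is at insertion. Section 5.3.2.F enumerates reasons only for weeks 13 to 26 after randomization. Randomization is at 13 weeks after insertion or later. For a woman randomized at week 30, a removal 3 weeks later falls at week 33 after insertion: after the first window closes and before the second opens. Section 5.3.1.g gives both post-randomization and post-enrollment limits for the survey at removal.

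**The case against.** The case against has four parts.

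- **The 4-week floor is not universal.** Sections 2.0, 5.3.2.A and 8.4 state the endpoint without it. That is correct, so the exclusion is strict only under 5.3.1.i. Those sections still do not say how a removed woman counts, so they do not supply the rule.
- **Early removals may be few.** The remarks in 4.0 and 5.2.1 on why implants are removed concern use of the method generally, not the 4 weeks after randomization. If removals were spread evenly over 13 weeks and 20% of failures left that way, s would be 0.20 × 4/13 = 6% and power 94%. It would take about 43–44% of failures leaving by removal to bring power below 90%. This stands, and it limits the size of the problem.
- **Section 8.3 foresees removal and allows extra enrollment.** More patients can restore precision, but they do not classify the women already removed.
- **The remedy creates a composite** that counts removals in weeks 0–4 but not bleeding reports in those weeks. This is a real cost.

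A reader might also infer from 8.4 ("though it may not be statistically significantly lower given the expected removal rate") that the sponsor expects few removals, and hence that 44% and 80% make sense only as total failure with removals included. The documents do not support this. Section 8.4 gives no removal rate, and a non-significant result could equally come from high but similar rates: 85% vs 75% has only 24% power with 50 per arm. Section 5.4.1 points the other way, since it has 66 women requesting and then receiving additional treatment.

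**Conclusion.** The point holds as a gap in the endpoint definition and the analysis rule. It is not an error in the power arithmetic. Under 5.3.1.i a woman removed for bleeding by week 4 cannot be a primary event, and nowhere does the plan say how a removal at any time enters the primary comparison.

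The effect depends on numbers the documents do not give. With equal shares scored as non-events, power stays at or above 90% up to about 13% of failures and is 85% at 20%. It is more sensitive to imbalance, with 3 placebo and 0 doxycycline giving 88%. A reader might infer that the missing rule can only dilute the treatment effect. It cannot be relied on to do so, because more early removals on doxycycline would exaggerate the benefit.

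On the planning rates, the supportable statement is limited. The 44% equals the cohort's removal-request rate, and the 80% is a judgment-based discount from its 92%. Section 5.4.1 presents both as requests for additional treatment without explaining the change of outcome. The gap should be closed before unblinding.

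**What to change.** Make one dated amendment before the unblinding described in 5.3.1.j.

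- **Scoring rule (5.3.1.i, 5.3.2.A, 5.4.2).** State that removal or a removal request for bleeding, from randomization to week 13, counts as treatment failure in the primary comparison and as an event in any Kaplan-Meier or Cox analysis. Keep all randomized women in the denominator.
- **Reporting.** Give the two components by arm: bleeding report after week 4, and removal for bleeding.
- **Sensitivity analyses.** Add one limited to events after week 4, and one that varies the scoring of removals for other reasons.
- **Planning rates (5.4.1).** State what 44% and 80% include. If they include removals, fewer women will remain for secondary treatment, so revise the expected 66 and the two ±10% precision statements that rest on it.
- **Reason for removal (2.0, 5.3.1.g, 5.3.2.F).** Reconcile the time windows so that the reason is recorded for every removal after randomization.

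The changes need no additional patients or visits. They may mean more data capture, because the present windows can miss the reason for an early removal in a woman randomized late. Enrollment is under way (7.1), so this is a mid-trial clarification of the primary endpoint and should be documented as made while blinded. It makes the endpoint a composite that treats removals and bleeding reports differently in weeks 0–4; the analysis limited to events after week 4 shows how much that matters.

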5.3.2 Outcome measurements

A. Primary treatment efficacy and safety end point (primary endpoint addressing specific aim #1)

- The efficacy of Doxycycline on ESI-related bleeding will be compared to placebo based on rates of **unacceptable bleeding** and weekly prospective symptom diary at 13 weeks post-randomization.

B. Primary treatment efficacy and safety endpoints (secondary endpoints addressing specific aim #1)

- Method continuation rate at 13 weeks post-randomization will be compared for women in the Doxycycline vs. placebo group.
- Bleeding patterns will be quantified based on the PBLAC and WHO classification of clinically important bleeding patterns over each 13 week reference period.[13,14, 29].
- Incidence of additional symptoms including acne, headache, mood changes in the treatment groups will be compared to placebo at randomization and 13 weeks post-randomization based on the weekly prospective symptom diary
- Interval to recurrence of unacceptable bleeding post-randomized treatment (i.e., need for additional treatment) will be determined
- Rate of adverse events associated with medical treatment will be documented by prospective symptom diary and BMI calculation. These include headache, mood changes, acne and change in BMI.

C. Patient satisfaction with primary treatment endpoint (primary endpoint addressing specific aim #2)

- Patient satisfaction with ESI at randomization for a baseline pre-treatment satisfaction and at 13 weeks post-randomized treatment following primary treatment with Doxycycline vs. placebo will be compared

D. Patient satisfaction with secondary treatment endpoint (primary endpoint addressing specific aim #2)

- Patient satisfaction with ESI at 26 weeks post-randomized treatment for patients with continued unacceptable bleeding following primary treatment who receive secondary treatment with Doxycycline will be calculated.

E. Secondary treatment efficacy and safety endpoint (primary endpoint addressing specific aim #3)

- Method continuation rate at 26 weeks post-randomized treatment for patients with continued unacceptable bleeding after primary treatment who undergo secondary treatment with Doxycycline will be calculated

F. Secondary treatment efficacy and safety endpoint (secondary endpoints addressing specific aim #3)

- Rate of ESI removal for bleeding between 13 and 26 weeks post randomization.
- Rate of ESI removal for reasons other than bleeding with enumeration of reasons for removal between 13 and 26 weeks post-randomization.
- Alternative contraception chosen if ESI removed will be documented.

5.4 Statistical Analysis:

Baseline demographic and clinical characteristics will be documented as detailed in section 5.3.1a patient enrollment.

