5.2.1 Patient selection

After appropriate IRB approval, ESI users aged 18-51 years old who meet the inclusion and exclusion criteria, and sign a written consent will be **enrolled in the study at the time of ESI insertion**. Every effort will be made to insert ESI on the same day as consent unless medically contraindicated. They will complete a prospective symptom diary from date of ESI insertion. All patients will be contacted by study personnel 13 weeks after enrollment and queried as to the presence of unacceptable bleeding. Bleeding concerns will be objectively assessed using a modification of the Pictorial Blood Loss Assessment Chart (PBLAC) [27]. Patient-initiated contact in with bleeding concerns at any time after 13 weeks post ESI insertion will result in enrollment and randomization at the time of contact. **The basis for randomized treatment will be whether or not the bleeding is “unacceptable” to the patient. This is inherently subjective, but constitutes the basis for most removal requests.** Patients who report unacceptable bleeding at 13 weeks post-ESI insertion, and those who call with bleeding concerns after 13 weeks post ESI insertion, will be randomized into two groups (Doxycycline or placebo). Patients who do not report unacceptable bleeding will continue to complete diaries and may be eligible for randomized treatment if unacceptable bleeding develops. Patients will receive diaries sufficient for completion of the study with instructions to contact study personnel if more diaries are needed or if diaries are lost. Patients and investigators will be blinded to the group assignment as well as the study coordinator who will be responsible dispensing of appropriate study medication by the pharmacy.

Patients who continue to have unacceptable bleeding after 4 weeks post-randomized treatment and wish to have secondary treatment will be treated with Doxycycline. Secondary treatment will not be blinded. Rates of unacceptable bleeding and patient satisfaction scores at 26 weeks post-randomized treatment in remaining study participants will be calculated.

[figure not shown]

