If a patient reports bleeding concerns as described in section 5.2.1 and is randomized to the placebo group, she will be given a pill bottle containing placebo made to look identical to treatment to be taken twice daily for 10 days. Patient and investigators will be blinded as to group assignment.

d. Doxycycline group

If patient has bleeding concerns determined in section 5.2.1 and is randomized to the Doxycycline group, she will be given a pill bottle containing Doxycycline 100 mg to be taken twice daily for 10 days. Patient and investigators will be blinded as to group assignment. Patients who experience unacceptable bleeding but are not bleeding at the time of study personnel contact will be instructed to call back if unacceptable bleeding recurs for randomization to treatment or placebo.

e. Treatment compliance process

Pill counts at the end of each treatment course will be performed to assess patient compliance with treatment. A pill diary given to patients at the time of randomization will provide temporal correlation between treatment initiation and bleeding symptoms.

f. Symptom recording

Upon enrollment and ESI insertion, patients will begin a weekly prospective symptom diary in order to self-assess bleeding and additional symptoms for a **total of 39 weeks from study enrollment**. A modification of the PBLAC where 1= no bleeding, 2=spotting requiring 1-2 panty-liners per 24 hours only, 3= bleeding requiring 1-3 tampons/pads in 24 hours, 4=bleeding requiring 4-6 tampons/pads per 24 hours, and 5=bleeding requiring >6 tampons/pads per 24 hours will be utilized for bleeding recording.[27] Bleeding diaries will be collected every 13 weeks and completion will be required for continued enrollment in the study and receipt of remuneration after every 13 week interval. Patients will also record any other associated symptoms such as headache, mood changes, acne and intolerance to treatment detailed in sections 6.2.2 and 6.2.3. Prospective symptom diary can be captured on a paper formate or via Mayo Clinic website RED Cap.

A bleeding episode is defined by the WHO as any set of one or more bleeding days (either consecutive or separated by only one bleeding-free day) bounded at each end by two or more bleeding-free days. **The bleeding pattern will be analyzed within each 13-week reference period** and categorized into 6 groups [4, 13, 14]:

- Amenorrhea (no bleeding during the reference period),
- Infrequent bleeding (fewer than 3 bleeding episodes),

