6.2.3 Anticipated Adverse Drug Reactions of Doxycycline

Serious side-effects include

- pseudotumor cerebri (rare)
- seizure
- swelling of face, lips, tongue, or throat
- headache
- wheezing
- chest tightness
- fever

Other side effects include

- abdominal pain
- Nausea or vomiting.
- Diarrhea
- loss of appetite.
- vaginal yeast infection
- skin itching and sensitivity to the sun
- cough

6.3 Reporting of Adverse Events:

All adverse events will be recorded on the case report forms. Serious adverse events forms must be completed and faxed to ESI clinical affairs within 3 days of knowledge of

the event. Unanticipated adverse device effect and/or unanticipated adverse drug reaction forms must be completed and faxed to ESI Clinical Affairs within 24 hours of knowledge of the event.

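### The between-arm safety comparisons have no on-treatment window, so open-label doxycycline and long follow-up dilute the effects of the 10-day randomized course

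*Combined protocol and SAP*

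**What the plan says.** **Endpoint.** Section 5.3.2 B, under the secondary endpoints for aim 1, states: "Rate of adverse events associated with medical treatment will be documented by prospective symptom diary and BMI calculation". It continues: "These include headache, mood changes, acne and change in BMI". This bullet gives no time point. A separate bullet covers additional symptoms (acne, headache, mood changes), which "will be compared to placebo at randomization and 13 weeks post-randomization based on the weekly prospective symptom diary".

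**Doxycycline reactions.** Section 6.2.3 lists headache among the serious reactions. Its other reactions include abdominal pain, "Nausea or vomiting", diarrhea, loss of appetite, vaginal yeast infection, "skin itching and sensitivity to the sun", and cough.

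**Capture.** Under section 5.3.1 f the diary also records treatment intolerance, by reference to section 6.2.3. Section 6.3 puts all adverse events on the case report forms.

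**Analysis.** Section 5.4.2 compares the presence of adverse events between arms by chi-square, with no period stated. It also models days with additional symptoms by Poisson regression, with each patient's whole diary follow-up as the offset. Section 7.1 continues the diaries to 26 weeks after randomization.

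**Exposure.** In the doxycycline arm, "she will be given a pill bottle containing Doxycycline 100 mg to be taken twice daily for 10 days" (section 5.3.1 d). Women in either arm with continuing unacceptable bleeding after 4 weeks who "wish to have secondary treatment will be treated with Doxycycline" receive it unblinded (section 5.2.1).

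**The concern.** The randomized contrast in drug exposure lasts 10 days. It stays free of open-label drug for about 4 weeks. After that, women in both arms may take doxycycline, and the plan expects more of them in the placebo arm. A safety comparison that runs past that point counts doxycycline reactions in the placebo arm as placebo events. One that averages over all diary days mixes a short exposed period with a long unexposed one. Both push a real difference toward no effect.

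The endpoint wording adds to this. Three of its four named items (mood changes, acne, change in BMI) are not on the section 6.2.3 list, while the gastrointestinal, skin and yeast reactions on that list are not named. BMI is a weak marker of a 10-day course: the values the plan describes are at enrollment (section 5.3.1 a) and at 26 weeks after randomization (section 5.3.1 j).

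At stake is the trial's randomized evidence on how well doxycycline is tolerated. A finding of no difference could reflect the choice of period and not the drug.

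**Working it through.** **The plan's figures.** No power or precision is stated for any safety comparison. The rates borrowed below are those of the primary power statement in section 5.4.1: 44% on doxycycline and 80% on placebo needing additional treatment, 50 per arm, two-sided 0.05. That calculation gives 97.0% power, which agrees with the stated figure of over 90%.

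**Possible open-label exposure.** 0.80 × 50 = 40 placebo patients and 0.44 × 50 = 22 doxycycline patients. These are upper figures, because secondary treatment depends on the woman's wish and the number treated before week 13 is not given.

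**Cumulative comparison to week 13.** Assumed, not in the documents: 5% event risk on placebo, 20% per doxycycline course, independent courses. Let f be the share of secondary courses that fall before week 13.

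- Placebo arm: 1 − 0.95 × (1 − 0.80 × f × 0.20)
- Doxycycline arm: 1 − 0.80 × (1 − 0.44 × f × 0.20)

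| f | Placebo | Doxycycline | Difference | Power, 50 per arm |
|---|---|---|---|---|
| 0 (window closes before open-label drug) | 5.0% | 20.0% | 15.0 points | 62% |
| 0.5 | 12.6% | 23.5% | 10.9 points | 29% |
| 1 | 20.2% | 27.0% | 6.8 points | 12% |

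**Other assumptions, f = 1.** Suppose instead that the 20% already includes the 5% background. The drug-attributable risk per course is then q = 1 − 0.80/0.95 = 15.8%, and the placebo arm reaches 1 − 0.95 × (1 − 0.80 × 0.158) = 17.0%.

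- If second courses add no new events, the doxycycline arm stays at 20.0%: a difference of 3.0 points, power about 6%.
- If they do, it reaches 1 − 0.80 × (1 − 0.44 × 0.158) = 25.6%: a difference of 8.6 points, power about 18%.

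**Symptom-day model.** Ten days is 10/91 = 11.0% of 13 weeks and 10/182 = 5.5% of 26 weeks. With an assumed on-treatment rate ratio RR and a constant background, the ratio over D diary days is (10 × RR + D − 10)/D. For RR = 3:

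- D = 91: (30 + 81)/91 = 1.22
- D = 182: (30 + 172)/182 = 1.11

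This is before any open-label drug. If each expected secondary user also took one 10-day course (an assumption) within the period, each course would add 20 day-equivalents:

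- D = 91: (91 + 20 + 0.44 × 20)/(91 + 0.80 × 20) = 119.8/107 = 1.12
- D = 182: (182 + 20 + 0.44 × 20)/(182 + 0.80 × 20) = 210.8/198 = 1.06

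**The case against.** The strongest reply is that the plan already has an adverse-event comparison. Section 6.0 defines adverse events broadly and without regard to cause, section 6.3 records all of them, and section 5.4.2 compares their presence between arms. The endpoint list is introduced as inclusive, so it need not be closed. This stands. A reader might infer that nausea, diarrhea or photosensitivity are left out of the analysis; the documents do not support that. The gap in the endpoint is one of naming.

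Three other readings are also too strong.

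- **That the adverse-event comparison is fixed at week 13.** The wording "will be compared to placebo at randomization and 13 weeks post-randomization" belongs to the additional-symptom bullet. The adverse-event bullet and the chi-square have no time point. Nor does the text say whether 13 weeks means a snapshot or everything up to then.
- **That a week-13 snapshot sets doxycycline against doxycycline.** If courses last 10 days, most women would be on no drug at that moment. The dilution by open-label drug applies to cumulative comparisons; a snapshot instead falls about 11 weeks after randomized dosing ends.
- **That the endpoint is a list of implant effects.** Headache is a listed doxycycline reaction, and section 4.0 gives weight gain, headaches and mood changes, but not acne, among reasons for implant removal. Section 6.2.2, which the plan cites, is not in the text available for this review, so how it classes the other items cannot be judged.

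It is also fair that the endpoint is secondary, that no safety power is claimed, and that section 8.4 expects few events. Even the clean window has only 62% power in the example. None of this supplies a window. Recording a reaction, or testing for its presence over an unstated period, does not separate the randomized course from later open-label courses.

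**Conclusion.** The concern holds as one of timing and naming. No section closes the between-arm safety comparison before open-label doxycycline begins, and the symptom-day model spreads a 10-day exposure over up to 182 diary days. Cumulative comparisons are therefore pulled toward no difference.

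The direction follows from the plan's own design and its 80% and 44% rates. The size does not: it rests on the assumed 5% and 20% event risks, on independent courses, and on how many secondary courses start before week 13. With all of them before week 13, 15 points become about 7, with 3 to 9 under the variants shown. With half of them, 15 become about 11. For symptom days, an assumed ratio of 3 falls to 1.22 over 13 weeks and 1.11 over 26 weeks before any open-label use.

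Severity is minor to moderate. The primary analysis is untouched.

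**What to change.** In sections 5.3.2 B and 5.4.2:

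1. Name the section 6.2.3 reactions in the treatment adverse-event endpoint.
2. Make the between-arm comparison, both the chi-square and the symptom-day model, over a prespecified window from the first randomized dose to week 4 or the start of secondary treatment, whichever comes first. Use the diary days inside that window as the model's offset.
3. Report events after secondary treatment separately, by randomized arm and without a test.
4. Keep mood changes, acne and BMI as additional symptom outcomes, and state whether the 13-week symptom comparison is a snapshot or cumulative.

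The cost is wording. The weekly diaries, pill diary and case report forms already collect what is needed, and treatment does not change. Section 5.3.1 j unblinds only after all patients finish, so the window should be fixed before then. The downside is that later events fall outside the randomized comparison and are only described.
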